**REMOTE (phone) COHORT:**

Additional information about assessments and measurements at in-person visit (baseline, 3, 6 and 12 months):

**2022 BUDGET CUT UPDATE:** As of March 31, 2022, neither the i-STAND cohort nor the control cohort will have a 12-month assessment

**Cardiometabolic biomarkers:** None

**Weight, Height, Waist.** Weight will be measured using the EtekcityEB9380H scale sent to participants from Amazon. The scale comes with a tape measure. Waist circumference will be measured twice at the superior border of the iliac crest and the average of two measurements used using instructions on how to take an accurate measurement sent by the research specialist.

**Blood Pressure:** We will measure blood pressure (systolic and diastolic) three times to ensure accurate results. BP will be measured using the Omron 3-Series BP7100 monitors, sent to the participant (along with cuff and instructions on use) from a third party vendor. Study measurement of blood pressure using these devices will be conducted during a phone call with the study Measurement RS, allowing for verbal instructions and questions from participants about the proper use of the device, including to avoid caffeine, tobacco and exercise in the 30 minutes prior to the visit to ensure accuracy.

**Demographics:** Age, sex, education, marital status, race/ethnicity, retirement status, and other pertinent demographics will be measured using self-reported items on the baseline survey. Some demographic variables will be used as covariates in analyses.

**Psychosocial and environmental measures:** We will measure self-efficacy based on modifying measures that were developed in youth and adults (since none exist for older adults) and habit formation which will be assessed using a modification of the Self-Report Habit Index (e.g., "sitting is something I do without thinking"). We have also included validated instruments to better assess participant psychosocial status in the current environment. This includes lower extremity items from the Late-Life Function and Disability Instrument (LLFDI) for physical function; Generalized Anxiety Disorder Assessment (GAD-2) and the Perceived Stress Scale (PSS) for stress/anxiety; and COVID-19 impact. As always, participants can choose not to answer questions on the survey that make them uncomfortable. This information will be used by the statistician to determine whether any of the COVID-19 related variables are moderators of the interventions.

**Physical function.** We will measure the chair rise sub-scale of the Short Physical Performance Battery as part of the remote assessments. The study RS will provide instructions and guidance to the participant via phone in order to conduct this measure remotely.

**Other behavior changes.** We will explore other activPAL metrics including sit-to-stand transitions, standing time, and step counts (as a measure of total physical activity). The same data-processing techniques will be used for these outcomes as for activPAL-measured sitting time. Self-reported

sedentary behaviors will be assessed with the Sedentary Behavior Questionnaire to understand what types of sedentary behaviors are amenable to change. This measure has acceptable test-retest reliability and convergent validity.

**Quality of life** will be measured with the PROMIS Global Quality of Life Scale The Patient Health Questionnaire-8 will assess depressive symptoms and levels improved in our pilot work.

### Device information

The activPAL (PAL Technologies Ltd, Glasgow, UK) is currently the most valid objective measurement of sitting time as it differentiates sitting from standing using an inclinometer and proprietary software to calculate time spent sitting/lying, standing, stepping, and number of sit-to-stand transitions. This device has been used with older adults, is sensitive to change and has high validity in comparison to direct observations. It is considered more valid for measuring sitting time and breaks from sitting than Actigraph or Actiheart accelerometers. We will use the activPAL micro which is unobtrusive, very light (10 grams), 5 mm thick, and worn on the thigh using a waterproof medical adhesive (Tegaderm™) that does not require skin preparation such as shaving. The device does not have to be removed. The research specialist will train participants in how to attach and replace the activPAL in the event the dressing becomes compromised or if skin irritation occurs. This training will ensure that I-STAND participants are able to independently apply the activPAL to their leg for interim activPAL wear. The device has worked well in [name] sub-study of over 1100 older adults enrolled in [name] Changes in Thought Study. Very few reports of difficulties or skin irritation have occurred.

The Fitness activity tracking band will be offered to i-STAND participants (not to the attention control group) for activity prompts at selected intervals. Participants can choose at any time to not use the band (some may not find the reminders useful). No data will be collected from the activity band itself. It is solely used as a prompting device for 15-minute reminders to stand.

### Direct identifiers that will be collected or included in the analytic data files, the linking file, or other study records (e.g., recruitment records, intervention files) at KP Washington.

DIRECT IDENTIFIERS		
 Names  Dates  Postal address  Geocode  Phone numbers  Fax numbers  Email address	 Social Security Numbers  Medical record numbers  Health plan numbers  Account numbers  License/Certificate numbers  Vehicle ID numbers  Device identifiers/Serial numbers	 Web URLs  IP address numbers  Biometric identifiers (e.g., finger prints, voice prints, retina scans)  Facial Photos/Images  CHS ID  Other unique identifier(s):

**Attention Control group:**  
ORIGINAL (in-person) COHORT:

This intervention was designed to control for a similar amount of contact time and attention, nonspecific treatment effects, study satisfaction, and patient expectations. Attention controls have been used in previous physical activity intervention trials among older adults for whom time, attention, and social support may be particularly salient factors that affect study outcomes. Attention control participants will receive the same number of contacts as i-STAND participants and a study workbook with general healthy living content based on the usual care available to KP members. During the initial in-person session, participants will choose up to 9 topics from a list of 17 to review with their health coach during subsequent sessions (see Table 2). The content provided will not include any information that could impact sitting time or physical activity. During the 9 follow-up calls, the health coach will review progress towards prior goals, engage participants in brief discussions of the session topic, and set goals for new topics. All health-related content included in the workbook and delivered by the health coach is currently available online to KP members and is reviewed and updated regularly by KP physicians. The attention control group will receive no further intervention after the 6-month measurement visit.

**REMOTE (phone) COHORT:**

This intervention was designed to control for a similar amount of contact time and attention, nonspecific treatment effects, study satisfaction, and patient expectations. Attention controls have been used in previous physical activity intervention trials among older adults for whom time, attention, and social support may be particularly salient factors that affect study outcomes. Attention control participants will receive the same number of contacts as i-STAND participants and a study workbook with general healthy living content based on the usual care available to KP members. During the initial phone session, participants will review with their coach the first 5 topics (topics for Sessions 1-5 are assigned to the participant). After the first 5 sessions, the participant can choose and additional 5 topics that interest them for Sessions 6 – 10 (see Table 2). The content provided will not include any information that could impact sitting time or physical activity. During the 9 follow-up calls, the health coach will review progress towards prior goals, engage participants in brief discussions of the session topic, and set goals for new topics. All health-related content included in the workbook and delivered by the health coach is currently available online to KP members and is reviewed and updated regularly by KP physicians. The attention control group will receive no further intervention after the 6-month measurement visit.

**Blinding (incomplete disclosure): Health coaching training, fidelity, and tracking.**

Health coaches will be trained and supervised by [name], a licensed clinical psychologist who has training in motivational interviewing, cognitive behavioral therapy, acceptance and commitment therapy, and behavioral activation. Training *for coaches* will include 8 hours of didactic information on principles of coaching, motivational interviewing, and the behavioral strategies to be employed in each condition. Coaches will receive detailed intervention phone scripts *for each condition* to enhance fidelity to intervention content. Coaches will undergo thorough practice of in-person and phone sessions including a final evaluation with attention control or i-STAND practice patients. To enhance fidelity, all phone calls will be audio-recorded and a random 10% will be reviewed by [name] for content

coverage using a study-specific checklist. *Any deviations from protocol will be rectified during health coach supervision which will occur weekly (separately).* Participants identified as having any concerning physical or mental health issues will be called by [name] or Drs. [name] or [name], the study physicians, who will seek participant permission to notify the participant's primary care physician of the concerns through the KPWA secure messaging system. All participant intervention contacts will be tracked using a tailored Microsoft Access database developed by a programmer. The Health Coaches will not be blinded. Only the research specialist will be blinded. The blinded research specialist who conducts measurements will not have access to the intervention tracking database.

As described on page 12 of this protocol, there is some blinding/incomplete disclosure to participants during the consent process.

### Procedures to monitor, lessen or mitigate risk

Use of KP Consulting Nurse Service as needed

Physician on call

Participants will be fully informed about the study

Risk of breach of privacy described further in section 5.f.

Risk of breach of security described further in section 7.

Data Safety Monitoring Plan in place: See DSMP for protocols around concerning health (mental and physical) risks as well as elevated BP, HbA1c.

### Subject drop out or withdrawal procedures

#### ORIGINAL (in-person) COHORT:

At any time, subjects can opt out of the study. Anyone who wishes to drop out will be called by their health coach to determine if they are still willing to provide measurement data, and a letter will be sent relevant to the timepoint in question. A participant may be dropped from the study if they state during the course of the study that they can no longer participate in calls and/or visits (for instance if they move). Participants may also be dropped if at some point their health has deteriorated to a point where their participation is no longer optimal (we are recruiting participating up to age 89 so some decline in general health as a result of age may occur during the year-long participation. This will result in the participant no longer being able to participate. This determination will be made by the PI. This is also described in the consent form.

#### REMOTE (phone) COHORT:

At any time, subjects can opt out of the study. Anyone who wishes to drop out will be called by their health coach to determine if they are still willing to provide measurement data, and a letter will be sent relevant to the timepoint in question. A participant may be dropped from the study if they state during the course of the study that they can no longer participate in calls. Participants may also be dropped if at some point their health has deteriorated to a point where their participation is no longer optimal (we are recruiting participating up to age 89 so some decline in general health as a result of age may occur during the year-long participation. This will result in the participant no longer being able to participate. This determination will be made by the PI. This is also described in the consent form.

**Anticipated study end date**

We anticipate completing all subject visits/phone calls by June 30, 2022. COVID-19 UPDATE: We anticipate this date extending to December 2022. We have notified our NHLBI program officer.

**a. Data Analysis**

Describe the data analysis plan, including:

- Statistical procedures.
- When applicable, the power analysis.
- Any procedures that will be used for quality control of collected data.

FOR BOTH ORIGINAL AND REMOTE COHORTS: We will add secondary analyses to address changes due to COVID-19.

*Preliminary analyses. The statistician will be blinded to intervention condition and intent-to-treat analyses will be performed.* Before analysis, data will be cleaned and checked for out-of-range and invalid values. We will examine the distribution of baseline covariates across groups to evaluate balance by randomization assignment. Further, we will compare follow-up rates by group assignment along with assessing for imbalance of baseline covariates by intervention group in the subset with follow-up outcome measures. Given the large sample size, we expect that between-group differences will be small. However, if factors differ by group at baseline, we will adjust for them in the final analyses or use them in imputation analyses if we have a larger than expected dropout rate. All analyses will be based on the “intent-to-treat” principle. Regardless of actual intervention participation, outcomes will be analyzed using the group to which participants were randomly assigned. We will also attempt to obtain follow-up data from all participants, regardless of participation level.

**Aim 1: Determine the efficacy of i-STAND to improve primary and secondary outcomes at 6 months.**

*Primary Outcome Analysis:* Our primary outcomes are change from baseline in mean daily sitting time and systolic and diastolic blood pressure (described in Section C12). We will compare group means for our primary outcomes between participants randomized to i-STAND versus attention control using linear regression with generalized estimating equations (GEEs) including both outcome time points at 3 and 6 months. GEE is used to account for multiple outcomes measured on the same study participant along with relaxing the normality assumption that standard linear regression methods require. We will adjust for baseline covariates including participant age, sex, physical function, and respective baseline outcomes with other covariates that are imbalanced in preliminary analyses. If dropout is above 15%, we will employ imputation techniques to address missing data issues. However, our focus will be on minimizing dropout rates. Analyses for secondary outcomes including lipids, fasting glucose, weight, and waist circumference will be similar, adjusting for respective baseline outcomes in the analysis. *Aim 2: Determine the maintenance of sitting and blood pressure reductions over 12 months.* We will conduct a sequential series of analyses using a similar statistical framework as outlined for Aim 1, but using 12-month follow-up data. We will first run a regression model with three groups (attention control, i-STAND no boosters, and i-STAND with boosters) including baseline covariates as outlined above. We will then

assess differences in primary outcomes at 12 months in the two i-STAND groups: with and without the booster intervention. If a significant difference in a given primary outcome is found in sitting time at 12 months between the i-STAND booster versus no booster groups (Scenario 1), we will further compare the i-STAND booster and no booster groups to the attention control group. Scenario 1 assessments will determine if i-STAND with boosters is better than i-STAND without boosters and if either or both I-STAND groups are better than attention control at 12 months.

If i-STAND groups do not differ at 12 months (Scenario 2), we will combine i-STAND groups and run a second regression model on each 12-month outcome including only attention control and i-STAND. If this regression shows that i-STAND has lower sitting time and/or blood pressure than attention control, we will conclude that the i-STAND intervention improved sitting time and/or blood pressure over 12 months, but boosters were not shown to be efficacious. We will conduct a similar analysis for secondary cardiometabolic risk marker outcomes.

**2022 BUDGET CUT UPDATE:** As of March 31, 2022, neither the i-STAND cohort nor the control cohort will have a 12-month assessment, so we are removing Aim 2. However, we will still explore maintenance of sitting and blood pressure reductions over 12-months for future grants and pilot data purposes.

**Aim 3: Explore moderators (e.g., age, sex, baseline physical activity) and mediators of reductions in sitting time (e.g., psychosocial variables) and cardiometabolic risk factors (e.g., changes in sitting time and/or physical activity).** Exploratory analyses will assess moderators of the intervention effect by including interactions with baseline variables such as age, sex, and physical activity level to determine if a subset of the population might be the best target for dissemination of the i-STAND intervention. If i-STAND is efficacious in reducing sitting time and/or blood pressure, we will also conduct mediator analyses to explore whether psychosocial or behavioral variables mediate the reduction in sitting time and/or blood pressure. All mediator analyses will only include mediators that are measured at time points prior to the outcome time measurement (e.g., 3-month mediators for 6-month outcomes) to assess for causal mediation relationships. We will take a forward stepped approach to assess 1) if a potential mediator is a mediator without including other potential mediators (bivariate mediator), and then 2) a multiple mediator analysis including all bivariate mediators in the model. This will allow us to assess if the mediation is independent of, or in combination with, other mediators. Finally, if i-STAND is efficacious in changing secondary cardiometabolic risk factors, we will explore whether reduced sitting time mediated these changes independent of increased physical activity. This analysis will provide important novel information on whether reduced sitting, regardless of changes in physical activity, can truly improve health among obese older adults.

**Additional exploratory analyses:** We will explore whether i-STAND improves standing time, breaks from sitting, physical activity (step counts), quality of life, physical function, and depressive symptoms. Further, per protocol analyses amongst those that adhered to the intervention will also be conducted. These analyses will use similar models as described for Aim 1 analyses.

**Power calculations.** Our sample size of 284 ensures 90% power to detect a difference in the reduction of sitting time between i-STAND and attention control of 41 minutes at 6 months (primary time point). Given our pilot results and i-STAND's long-term goal target of a 2 hour reduction in sitting time, a difference in sitting time reduction of 41 minutes is achievable. We assumed a standard deviation (SD)

in change in sitting time of *97 minutes/day based on I-STAND pilot RCT data*, a pooled sample t-test, and a 15% loss to follow-up under which we would observe 241 participants at 12 months. *Further, this sample size provides 90% power to detect a difference of 6.2 mmHg change in systolic (14.7 SD) and 4.0 mmHg change in diastolic (9.5 SD) blood pressure. We are powered for comparable reductions in blood pressure as those observed in walking and exercise interventions (5-10 change in systolic and 1-6 mmHg change in diastolic blood pressure). Therefore, we are powered to achieve a minimal clinically important difference for blood pressure outcomes.*

For Aim 2, we will have 90% power to detect a 58-minute difference in sitting time between i-STAND with boosters compared to i-STAND without boosters at 12 months. Further, given Scenario 2 in which i-STAND boosters is not different than i-STAND without boosters we will have 90% power to detect a 41-minute difference in sitting time with combined I-STAND groups. Given Scenario 1, in which i-STAND with boosters is significantly different from i-STAND without, at 12 months, we will have 90% power to detect a 50-minute difference in sitting time between either i-STAND group and the attention control. *For blood pressure outcomes, we have 90% power to detect an 8.8 mmHg change in systolic blood pressure and 5.7 mmHg change in diastolic blood pressure when comparing i-STAND groups (booster vs. no booster) at 12 months.* Therefore, this study is well powered to address all aims.

**2022 BUDGET CUT UPDATE:** As of March 31, 2022, for Aim 2, assuming we have 124 participants completing 12-month outcome follow-up, we will have 90% power to detect a 81-minute difference in sitting time between I-STAND with boosters compared to I-STAND without boosters at 12 months. Further, given Scenario 2 in which I-STAND boosters is not different than I-STAND without boosters we will have 90% power to detect a 57-minute difference in sitting time with combined I-STAND groups. Given Scenario 1, in which I-STAND with boosters is significantly different from I-STAND without, at 12 months, we will have 90% power to detect a 70-minute difference in sitting time between either I-STAND group and the attention control. For blood pressure outcomes, we have 90% power to detect an 12.3 mmHg change in systolic blood pressure and 8.0 mmHg change in diastolic blood pressure when comparing I-STAND groups (booster vs. no booster) at 12 months. We acknowledge we will likely be underpowered for Aim 2 and this is why we have now made it exploratory.

b. Sharing of Results with Subjects

Describe whether results (study results or individual subject results, such as results of standard or research lab tests and genetic tests) will be shared with subjects or their providers.

If the study carries a risk of incidental findings, describe your plan for evaluating these and determining whether and how subjects or their providers will be given this information.

If laboratory results will be shared with subjects or their healthcare providers, verify that the laboratory conducting the test is Clinical Laboratory Improvement Amendments (CLIA) certified.

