**Purpose:**

Healthy Aging Resources to Thrive (HART) intervention focuses on reducing sitting time by standing more and breaking up prolonged bouts of sitting throughout the day. Because older adults with obesity rarely engage in physical activity, helping them sit less throughout the day could be a meaningful, but untested, health-promoting behavior. We will target a group with high prevalence of cardiometabolic conditions in which we have the opportunity to see the largest improvement in biomarkers related to cardiometabolic risk. We will conduct an efficacy randomized controlled trial to determine whether a sitting reduction intervention, improves behavioral and health outcomes to a greater extent than an attention-control group. The primary end point is 6 months. but participants randomized to the i-STAND intervention will be re-randomized at 6 months to either receive no further contact or a booster session intervention. Everyone will be followed until 12 months after baseline.

**2022 BUDGET CUT UPDATE:** As of March 31, 2022, participants randomized to the i-STAND intervention will no longer be re-randomized at 6 months. We will no longer follow participants to the 12-month timepoint and will end all activities after the 6-month timepoint.

The specific aims of the study are to:

Aim 1: Determine the efficacy of i-STAND to improve primary and secondary outcomes at 6 months.

Our primary outcomes are change from baseline in mean daily sitting time and systolic and diastolic blood pressure. We will compare group means for our primary outcomes between participants randomized to i-STAND versus attention control ("Healthy Lifestyles") at 6 months. Secondary outcomes include cardiometabolic biomarkers (HbA1c,), weight, height, and physical function.

Aim 2: Determine the maintenance of sitting and blood pressure reductions over 12 months.

We will then assess differences in primary outcomes at 12 months in the two i-STAND groups: with and without the booster intervention.

**Hypothesis 2:** i-STAND participants randomized to receive booster sessions will have reduced sitting time and improved cardiometabolic risk factors at 12 months compared to i-STAND participants receiving no further intervention and compared to the Healthy Lifestyles/attention control participants.

**2022 BUDGET CUT UPDATE:** As of March 31, 2022, we are cutting Aim 2 so as to conserve funds to focus on Aims 1 and 3.

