**2022 BUDGET CUT UPDATE:** As of March 31, 2022, we are no longer collecting measures at 1 year.

b. Preliminary Data

Describe any relevant preliminary data.

Our main preliminary study was a recently completed pilot RCT in obese adults over age 60 (PI: [name]). We found high levels of acceptability and excellent adherence. Sitting significantly reduced and standing significantly increased for those receiving the intervention.

**Table 1.** Preliminary sitting reduction studies from the study team

Study & design	Intervention(s)	Results	KPWA IRB Info
[name]  Randomized pilot over 3 weeks (N = 30; aged 50-70, Mean BMI = 27, 50% working, 50% retired)	Group 1: Increase standing time using standing desks. Group 2: Increase breaks from sitting using prompting strategies. Both met in-person weekly with health educator.	Group 1: -130 min/day in activPAL sitting time (p < .01) Group 2: +40 activPAL breaks from sitting/day (p < .01) High intervention satisfaction and adherence	N/A
[name]  One-arm pre-post pilot over 8 weeks (N = 25; mean age = 71, mean BMI = 34, 28% diabetes, 48% hypertension, baseline activPAL sitting = 9.2 hours/day)	Five phone calls from health coaches, activPAL feedback after baseline and at 4 weeks, goal-setting, problem-solving, motivational interviewing, relapse prevention, cues, self-monitoring	ActivPAL sitting -27 minutes/day, standing +20 mins/day; accelerometer MVPA +24 mins/wk (p's < .05) improved Improved gait speed, depressive symptoms (p's < .05), & weight (p = .07) Among those with SBP > 120, SBP (-6.8 mmHg, p = .06) & DBP (-3.0 mmHg, p < .05) reduced High phone call adherence and study satisfaction	417643-14: Take Active Breaks from Sitting Pilot (TABS-P) Study
[name] pilot RCT Randomized controlled pilot over 3 months (N = 60, mean age = 68, mean BMI = 36, 23% diabetes, 60% hypertension, mean baseline activPAL sitting = 10.2 hours/day)	Built on findings from our prior study and included 2 in-person sessions, 4 phone calls, activPAL feedback at baseline and 6 weeks, activity band to cue reminders to take breaks from sitting, and home environment audits	activPAL sitting (-54 for I-STAND vs. control, p < .05) and standing (+42 minutes/day for I-STAND vs. control, p < .01) improved  Adherence to sessions was 99%, high study satisfaction	817486-20: iSTAND R21

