## Data, sources, and date range

The following table shows how outcomes data will be collected

Source (specify) (i.e., from KPWA, or from an existing or previous study)	Key Information/Description of Variables	Date Range
---	--	------------

activPAL activity monitor	PRIMARY OUTCOME 

• Change in mean daily sitting at 6 months

	Baseline to 6-months
ORIGINAL COHORT: In-person measurement visit at KPWHRI  COVID-19 UPDATE AND NEW REMOTE COHORT REMOTE MEASUREMENT	PRIMARY OUTCOME 

• Change in systolic and diastolic blood pressure

	Baseline to 6-months
In-person measurements collected at clinic visit at KPWHRI  COVID-19 UPDATE AND NEW REMOTE COHORT: REMOTE MEASUREMENT OF WEIGHT	SECONDARY OUTCOMES 

• Change in HbA1c (Original Cohort only)

• Change in Weight

	Baseline to 6 months
In-person measurements collected at clinic visit at KPWHRI  COVID-19 UPDATE and REMOTE COHORT: REMOTE MEASUREMENT OF WEIGHT and BP	OTHER EXPLORATORY OUTCOMES for i-STAND BOOSTER ONLY 

• Change in HbA1c (original cohort only)

• Change in Weight

• Change in systolic and diastolic blood pressure

	Baseline to 12 months
activPAL activity monitor	OTHER EXPLORATORY OUTCOMES for i-STAND BOOSTER ONLY 

• Change in time spent sitting or lying down

• Change in step counts

	Baseline to 12 months
Participant questionnaire	OTHER EXPLORATORY OUTCOMES 

• Change in quality of life

• Change in depressive symptoms

	Baseline to 6 months

	
 
• Change in physical function
 
	
VDW	
Various chronic conditions (e.g. diabetes, cardiovascular conditions); lab values for HbA1c, cholesterol; blood pressure; blood pressure medications; height and weight; medical events (e.g. falls, hospitalizations, heart attack, stroke, blood clots); and, healthcare costs.
	
One year prior to first Study Visit date to the end of the study for up to 5 years after the study ends, no later than June 1, 2028

**2022 BUDGET CUT UPDATE:** As of March 31, 2022, neither the i-STAND cohort nor the control cohort will have a 12-month assessment to collect the outcomes listed in the table above. To be as clear as possible - those items have been highlighted in green.

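### Aim 1 has three unranked primary outcomes, no stated alpha and no rule for which result makes the trial positive

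*Combined protocol and SAP*

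**What the plan says.** Section 5a (Data Analysis, Aim 1) states: "Our primary outcomes are change from baseline in mean daily sitting time and systolic and diastolic blood pressure". Section 1 (Objectives) lists the same outcomes and adds: "We will compare group means for our primary outcomes between participants randomized to i-STAND versus attention control". Section 3 (Study Design) also treats sitting time and blood pressure as primary. The outcomes table in section 5 labels two rows as primary, one for sitting time and one reading "Change in systolic and diastolic blood pressure". None of these places ranks the outcomes.

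The power paragraph in section 5a takes 6 months as the primary time point and 284 randomised, with 241 observed after 15% loss. It gives 90% power for 41 minutes of sitting time (SD 97). It then says that "this sample size provides 90% power to detect a difference of 6.2 mmHg change in systolic (14.7 SD) and 4.0 mmHg change in diastolic" blood pressure (SD 9.5), and concludes that "we are powered to achieve a minimal clinically important difference for blood pressure outcomes".

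The plan gives no alpha, sidedness, testing order, alpha split or joint success rule for Aim 1. It numbers a Hypothesis 2 for the dropped Aim 2 but states no hypothesis for Aim 1. The only current text that bears on how efficacy is judged is the condition for the exploratory Aim 3 work: "If i-STAND is efficacious in reducing sitting time and/or blood pressure, we will also conduct mediator analyses".

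**The concern.** With three primary outcomes at three full-size tests, the plan has to say what counts as a positive trial. Here it could mean sitting time alone, any one of the three, either blood pressure measure, or all three. These readings have different error rates and different power, and the choice could be made after the results are known.

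Blood pressure is the most exposed. The plan presents it as powered in its own right, and it is the health outcome. If the intervention reduces sitting time, as the pilot RCT suggests (Table 1: "activPAL sitting (-54 for I-STAND vs. control"), the remaining question is whether blood pressure moves, and that question gets two unadjusted tests.

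Aim 3 is a lesser issue because it is exploratory, but its condition depends on the intervention being efficacious and that term is never defined.

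**Working it through.** **Inputs.** From the power paragraph: 284 × 0.85 = 241.4, so 241 completers, taken as 120 and 121 because allocation is 1:1; pooled t-test; differences and SDs of 41 (97) min, 6.2 (14.7) mmHg and 4.0 (9.5) mmHg. The plan ties the 241 to 12 months; it is used here for 6 months, as the plan's own figures require. Assumed, because the plan gives no values: SBP-DBP correlation 0.5-0.8 and sitting-BP correlation 0-0.3.

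**Reproducing the 90%.** The standard error is SD × √(1/120 + 1/121) = SD × 0.1288. Approximate power is Φ(difference/SE − z), with z = 1.960 at two-sided 0.05.

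| Outcome | SE | Difference/SE | Power, normal | Power, t |
|---|---|---|---|---|
| Sitting | 12.50 | 3.281 | Φ(1.321) = 90.7% | 90.5% |
| SBP | 1.894 | 3.274 | Φ(1.314) = 90.6% | 90.3% |
| DBP | 1.224 | 3.268 | Φ(1.308) = 90.5% | 90.2% |

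Other levels do not fit. With the same 241 completers, two-sided 0.025 gives about 84-85%, two-sided 0.0167 (0.05/3) about 80-81%, and one-sided 0.05 about 95%. Analysing all 284 at two-sided 0.025 also gives about 90%, but the plan says its figure assumes 15% loss. So each outcome was given an unsplit two-sided 0.05 (equivalently one-sided 0.025).

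**Error if any one result counts and nothing works.**
- Either direction, independent outcomes: 1 − 0.95³ = 14.3%.
- Either direction, trivariate normal simulation: 13.6% at SBP-DBP 0.5 and 12.4% at 0.8 (sitting-BP 0); 13.2% and 12.1% with sitting-BP 0.3.
- Benefit only: 1 − 0.975³ = 7.3% if independent, falling to 6.1% at correlations 0.8 and 0.3. The per-test rate is 2.5%.

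**Error on blood pressure if sitting time truly falls and blood pressure does not.**
- Either direction: 1 − 0.95² = 9.8% if independent; 9.1% at SBP-DBP 0.5 and 7.8% at 0.8.
- Benefit only: 1 − 0.975² = 4.9% if independent, falling to 3.9% at 0.8.

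**Power under an explicit rule.** Simulated t statistics, blood pressure at its planning differences, sitting time independent of blood pressure, SBP-DBP correlation 0 to 0.8. The fixed sequence tests sitting, SBP and DBP in turn, each at 0.05. Holm compares the ordered p-values with 0.0167, 0.025 and 0.05.

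| True sitting effect | Sequence: sitting / SBP / DBP | Holm: SBP |
|---|---|---|
| 41 min (planned) | 90% / 82% / 74-78% | 87-89% |
| 54 min (pilot RCT) | 99% / 89% / – | 88-89% |
| 27 min (one-arm pilot) | 58% / 52% / – | 85-86% |

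Holm power for sitting time at 41 min is about 89%. In Holm's worst case (0.0167 each), power is 80-81% and the differences detectable with 90% power rise to 46.2 min, 7.00 mmHg and 4.53 mmHg, from 40.7, 6.16 and 3.98 at 0.05. The 27-minute row uses a within-group change (Table 1: "ActivPAL sitting -27 minutes/day") as if it were a between-group effect; it only shows sensitivity.

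**The case against.** Several points can be made for the plan.

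- **Sitting time is always listed first.** This is an informal lead, but not a stated hierarchy, and the power text makes a separate claim for blood pressure.
- **The purpose could be read as needing both behaviour and health to improve.** On an all-three rule no alpha split is needed. But joint power is then about 74% if the outcomes are independent and about 80% at correlations 0.8 (SBP-DBP) and 0.3 (sitting-BP), not 90%.
- **Sitting and blood pressure could be separate questions, each with its own claim.** The plan does not say this, and blood pressure would still have two tests.
- **14.3% overstates the realistic risk.** Fair: it assumes independence and counts harmful results. The false-benefit figures are the ones to weigh for a trial of improvement, and they still exceed 2.5%.
- **The statistician is blinded to condition.** This limits bias in the analysis but does not define success.
- **Other text might supply a rule.** The GEE sentence deals with repeated measures at 3 and 6 months. The sequential scheme belongs to the removed Aim 2 and concerns booster groups. The pointer to a Section C12, which is not in the document, is attached to the description of the outcomes.
- **The power figures are simplified.** They use an unadjusted t-test, whereas the planned baseline-adjusted GEE may have more power. Taking sitting-BP correlation as 0.3 moves the fixed-sequence figures by one to three points (SBP 83%, DBP 77-79% with SBP-DBP 0.5-0.8; SBP 54% at 27 min).

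These points qualify the size. None supplies the missing rule.

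**Conclusion.** The concern holds and must be fixed. The plan names three primary outcomes, implicitly gives each a full two-sided 0.05, and does not define success for Aim 1. If one nominally significant result is enough, the chance of a false primary finding under the complete null is about 12-14% in either direction and about 6-7% for benefit. With a real sitting-time effect, the false blood pressure rate is 7.8-9.8% in either direction and 3.9-4.9% for benefit.

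The 0.05 level is inferred from the power figures. The correlations are assumed, so the ranges are not firm bounds. The inflation depends on the any-one-counts reading, which the plan neither adopts nor excludes. The absence of a rule depends on none of these.

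**What to change.** Before unblinding, add one paragraph to section 5a that states a family-wise two-sided 0.05 for the 6-month primary outcomes and adopts one of these rules:

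1. **Fixed sequence:** sitting time, then SBP, then DBP, each at 0.05, stopping at the first non-significant result. Sitting-time power stays at 90%. The cost falls on blood pressure, and no blood pressure claim is possible if sitting time fails.
2. **Holm across the three.** All three lose a little power, but a blood pressure claim does not depend on sitting time.

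The choice turns on the sitting effect the team expects. Near the pilot RCT's 54 minutes the two rules are almost equal for SBP; at a much smaller effect Holm protects blood pressure far better.

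Restate the power figures under the chosen rule, and define efficacious in the Aim 3 condition by the same rule. If unblinding has already taken place, report the rule as set afterwards. The cost is the paragraph and the revised power figures; no added participants or data are needed.
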